The predominant mode of addressing this excess burden of PCa to date has been through promoting screening in minority men; recent guideline changes suggest that this approach is no longer a viable option.¹¹ Tailoring treatment decisions for those patients with intermediate and high-risk PCa who may benefit most from definitive treatment, while informing patients with low-risk PCa about active surveillance and eliciting and respecting the values of all patients, represents a viable alternative strategy to reduce this excess burden.

PCa disproportionately affects African-American (AA) and American Indian/Alaska Native (AI/AN) men. Previous studies suggest that AA men have a higher incidence of more aggressive or advanced stage PCa and cancer-specific mortality compared to the general population.¹²⁻¹⁵ Native Americans from the Northern and Southern Plains also experience disparities in PCa stage and survival comparable to AA men; PCa is also the second leading cause of cancer-related mortality in Native American men overall.^{16,17} AI/AN men from these regions experience greater PCa mortality than non-Hispanic whites.¹⁷ In Hispanic/Latino men disparities are less clear. In general, although national data do not suggest major outcome disparities in this group, local and regional studies, as well as patterns of care studies review pockets of disparities particularly related to delays in care or different treatment patterns for Hispanic/Latino men.¹⁸⁻²³

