1.2 Study Goals

The long-term goal of this research is to reduce the excess burden of prostate cancer and the morbidity associated with its treatments. The overall objective is to test feasible, effective tools that promote SDM for prostate cancer initial treatment decisions, and which improve those decisions in a manner that is risk-concordant and patient-centered for minority men. Our aim is to test the comparative effectiveness of two kinds of decision aids – during consultation and pre-consultation – alone and in combination to improve patient knowledge, symptom burden, and risk-concordant treatment utilization in localized prostate cancer.

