1.3 Significance

This study will test the efficacy of decision aids in specialty practices that treat above average numbers of African American and Native American men and compare their impact in these populations to the general population within the infrastructure of the NCORP CCDR components. We hypothesize that decision aids will mitigate disparities related to poor patient-provider communication by improving knowledge, reducing burden of functional outcomes, as well as aligning treatment patterns with disease risk in these minority populations. This study is innovative because it tests newer tools, in newer formats, including within the clinical visit context, and with a novel trial design. It tests decision aids delivered within the clinical visit using a tablet format alongside a web-based decision aid delivered prior to the clinical visit. This study design represents a substantial departure from previous approaches by testing the comparative effectiveness of two prostate cancer decision aids in a 2x2 factorial cluster-randomized design within the NCORP CCDR components that looks at the individual and additive impact of those tools. This context will enable us to deliberately over-sample minority men. Knowing whether decision aids work at all, or which modes and contexts of decision aid delivery work best to improve communication are compelling health care delivery questions for the care of minority men facing the difficult choice of prostate cancer treatment. This study would be the first to bring decision aid research to the healthcare of Native American men; and would be only the second trial that we are aware of to test decision aids specifically in African American men. When complete, this strategy will produce significant generalizable inferences about the best way(s) to improve health service delivery to help address prostate cancer disparities.

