4.5 Stratification and Treatment Assignments

While not formal stratification factors, randomization will be set up so that sites will the particular capacities to oversample minority populations will be distributed between the arms, as illustrated in the diagram below.

Grouping Factors/Treatment assignments:

- Arm 1: Pre -and During Consultation Decision Aids
- Arm 2: Pre-Consultation Decision Aid only
- Arm 3: During Consultation Decision Aid only
- Arm 4: Usual Care

5.0**STUDY CALENDAR**

Laboratory and clinical parameters during treatment are to be followed using individual institutional guidelines and the best clinical judgment of the responsible physician. It is expected that patients on this study will be cared for by physicians experienced in the treatment and supportive care of patients on this trial.

Pre-Study Testing Intervals

- To be completed \leq 28 DAYS before registration: History and physical.
- To be completed \leq 90 DAYS before registration: PSA
- To be completed \leq 4 MONTHS before registration: Prostate Biopsy

	Prior to Registration	Baseline*	12 months after baseline**
Test and Observations			
History and Physical	X		
Height	X		
Weight	X		
Prostate biopsy	X		
Chart Review			X(1)
Labs and Staging			
PSA	X		
QOL Instruments			
Baseline Questionnaire		X(2)	
One-year Questionnaire			X(3)

* To be administered following the surgical consultation

** +/- 6 weeks

- 1 At 12 months site staff will review the patient's chart from the 6-month point to the 12-month time-point, collecting treatment information and any pertinent events.
- 2 Includes the Prostate Cancer Treatment Questionnaire and the Decisional Conflict Scale. See Section 10.0 and Appendix I.
- 3 Includes Expanded Prostate Cancer Index Composite (EPIC-26) and the Decisional Regret Scale. See Section 10.0 and Appendix II. To be completed by the patient during a clinic visit. If no clinic visit is scheduled +/- 6 weeks from the 12-month time-point, study staff should mail the 12-month questionnaire with a self-addressed stamped envelope to the patient for him to complete at home and return by mail (see Section 8.3.1).

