8.3.2 Twelve-month follow-up chart review

At this time site staff will also conduct retrospective chart review to ascertain treatment utilization and complete the follow-up form. Treatment utilization will be categorized by the type of treatment the patient had (surgery vs. radiation vs. active surveillance).

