12.4.2 Secondary analyses

Decisional quality, average clinical time required, and patient QOL scores will be compared across DA types using linear mixed models similar to that used to assess the primary endpoint. In particular, this model will include fixed effects for Prostate Choice and Knowing Your Options and a random, site-specific intercept to allow for subjects within the same site to be correlated. Utilization will be compared across DA types using a generalized linear mixed model, again with fixed effects for having received Prostate Choice and having received Knowing Your Options and a random, site-specific intercept.

As mentioned above, the primary analysis will be re-implemented within only minority men as a secondary analysis. We anticipate enrolling approximately 80% minority men. It is worth noting that, if this were the primary analysis, this sample would give us approximately 78% power to detect an absolute difference of 8% in knowledge for either of the decision aid main effects using a two-sample t-test (with two-sided alternative) with a 2.5% significance level (i.e. the same analysis/assumptions used to power the primary analysis).

As an additional secondary objective, we will explore whether the overall effects of interventions on patient knowledge, quality of life, and treatment utilization differ by racial/ethnic subgroups. Our sample size is driven by the primary outcome of knowledge. Oversampling of minority populations of interest will achieve a robust representation of these minority populations in our final sample, but we have not designed the trial to have sufficient power to ascertain subtle subgroup differences in knowledge and quality of life by race/ethnicity subgroups. These secondary analyses will be exploratory, because fully testing the racial/ethnic differences would require prohibitively large sample sizes, and the literature does not suggest a strong race-based rationale for large differences. If subtle but potentially important trends in subgroup differences are identified in these exploratory analyses, those findings could be used to justify a larger study examining a primary hypothesis related to racial/ethnic difference or could influence the design of subsequent culturally tailored interventions. At present, the science of decision aids and the state of the evidence surrounding racial/ethnic differences in the effect of decision aids would not support testing such a hypothesis as a primary endpoint.

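### Matching treatment to disease risk is a stated aim, but no risk-specific analysis of treatment utilization is committed, so shifts that differ by risk can be masked

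*Combined protocol and SAP*

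**What the plan says.** **Aim.** Section 1.2 says that the aids are tested for their ability to "improve patient knowledge, symptom burden, and risk-concordant treatment utilization in localized prostate cancer". Section 1.3 hypothesises "aligning treatment patterns with disease risk in these minority populations". The rationale in 1.1 gives the directions: "Tailoring treatment decisions for those patients with intermediate and high-risk PCa who may benefit most from definitive treatment" on one side and "informing patients with low-risk PCa about active surveillance" on the other.

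**Objectives.** Objectives 2.2.1 to 2.2.3 name treatment utilization without mentioning risk.

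**Endpoint.** Sections 8.3.2 and 12.4.1 classify utilization by the kind of treatment received. The three classes in 8.3.2 are surgery, radiation and active surveillance.

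**Model.** Section 12.4.2 states: "Utilization will be compared across DA types using a generalized linear mixed model". Its terms are a fixed effect for each aid and a random site intercept. The section does not say how three categories enter the model. The only effect modifier named for utilization is race/ethnicity.

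**Optional covariate.** Section 12.2.1 lists severity of disease among characteristics that may be added to the primary model at the analyst's judgement, and says that secondary endpoints will be handled in a similar way.

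**Population.** Section 3.2 admits Gleason 6-10, stage T1-3 and PSA below 50 ng/mL, so low- to high-risk disease is enrolled.

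**Chart review.** Footnote 1 of the section 5.0 calendar has staff review the "chart from the 6-month point to the 12-month time-point". Section 8.3.2 describes a retrospective review with no start limit.

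**The concern.** The rationale expects the aids to move treatment differently by risk: towards surveillance in low-risk men where that suits them, and towards definitive treatment in men at higher risk. A model with one effect per aid averages over these groups. An aid that worked as hoped in both could show little or no overall change. A shift confined to one group would appear as an overall change that cannot be read as better or worse alignment with risk.

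What is at stake is the interpretation of a secondary endpoint. The trial could report shares of each treatment by aid, but not whether either aid brought treatment closer to disease risk, which is one of its declared purposes.

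**Working it through.** The documents give no rate, effect size or power for utilization, so there is no figure of the plan's own to reproduce. All surveillance rates and risk shares below are assumptions.

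**1. Overall change as a weighted mix.** Let w be the low-risk share. Overall surveillance = w × (rate in low-risk) + (1 - w) × (rate in high-risk). Assume that an aid moves surveillance from 50% to 70% in low-risk men and from 30% to 10% in high-risk men.

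| w | Without aid | With aid | Change |
|---|---|---|---|
| 30% | 0.3×50 + 0.7×30 = 36% | 0.3×70 + 0.7×10 = 28% | -8 points |
| 50% | 0.5×50 + 0.5×30 = 40% | 0.5×70 + 0.5×10 = 40% | 0 |
| 70% | 0.7×50 + 0.3×30 = 44% | 0.7×70 + 0.3×10 = 52% | +8 points |

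The shift is 20 points in each group throughout. Only the case mix changes the overall figure and its sign.

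**2. Unequal shifts.** Keep 50% to 70% in low-risk men, but let high-risk men go from 10% to 5%. At w = 50% the overall rate moves from 0.5×50 + 0.5×10 = 30% to 0.5×70 + 0.5×5 = 37.5%, a change of +7.5 points. Masking is then partial.

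**3. Does the optional severity covariate help?** A logistic model with aid and risk as main effects matches the observed surveillance total in each aid group and each risk group. With the rates of step 1 and w = 50%:

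- Totals by aid: 40% and 40%.
- Totals by risk: (50 + 70)/2 = 60% in low-risk men and (30 + 10)/2 = 20% in high-risk men.
- Fitted values of 60% (low) and 20% (high), the same with and without the aid, meet all four totals, since (60 + 20)/2 = 40.

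The adjusted odds ratio for the aid is therefore 1.00. The odds ratios within risk group are (0.7/0.3)/(0.5/0.5) = 2.33 and (0.1/0.9)/(0.3/0.7) = 0.26.

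Large-sample fits at a second set of assumed rates (40% to 60% in low-risk men, 25% to 5% in the others; site intercept left out) agree. The odds ratios within risk group are 2.25 and 0.16.

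| w | Unadjusted OR | OR adjusted for risk as main effect |
|---|---|---|
| 40% | 0.82 | 0.80 |
| 50% | 1.00 | 1.00 |
| 60% | 1.19 | 1.22 |

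A main effect leaves the masking in place. An interaction, or an outcome coded by risk, removes it.

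**4. What a risk-specific analysis could detect.** Use the second set of rates and score each man 1 for surveillance if low-risk, or for surgery/radiation otherwise. At w = 50% this score goes from 0.5×40 + 0.5×75 = 57.5% to 0.5×60 + 0.5×95 = 77.5%. Each main effect compares 172/2 = 86 with 86 men. At an assumed two-sided 5% level, power is 0.81 without clustering. The mean site size is 172/20 = 8.6. If the intra-site correlation of 0.1, which the plan gives only for knowledge, also holds here, the design effect is 1 + (8.6 - 1)×0.1 = 1.76 and power is 0.56. For w from 30% to 70% the ranges are 0.86 to 0.77 and 0.62 to 0.52. The score serves only to gauge precision. It is not the proposed endpoint.

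**The case against.** - **The model answers the listed objectives.** This stands. Objectives 2.2.1 to 2.2.3 ask about treatment utilization and 12.4.2 compares it. A reader might infer that the analysis fails its own objective, but the documents do not support that. The gap is between the goals in 1.2 and 1.3 and what the objectives and analysis carry forward.
- **Disease risk is not wholly absent.** This also stands, because 12.2.1 allows severity of disease to be added. But the clause is optional and describes a covariate, and step 3 shows that a main effect does not help.
- **Exact cancellation is a special case.** Correct. It needs particular rates and a particular mix, and the documents give neither. A reader might infer that real effects will vanish; all that can be said is that they can be masked, fully or partly.
- **Intermediate risk has no single expected direction.** Section 1.1 groups these men with high risk in one place and lists surveillance, radiation and surgery as acceptable for them in another. This limits any concordance score, but not estimates by risk group.
- **Chart review.** A reader of the calendar footnote might infer that treatment in the first six months is not collected. Taken literally, and with no earlier review scheduled, the footnote would leave it out. But 8.3.2 has no start limit, and 12.4.1 defines utilization from the review at 12 months. The documents establish an inconsistency, not an omission.

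**Conclusion.** A stated aim of the trial has no committed analysis. As written, the plan can compare treatment shares by aid but cannot show whether treatment moved in line with disease risk, and the optional severity covariate does not change that. Under the assumed 20-point opposite shifts, the overall change runs from -8 to +8 points as the low-risk share goes from 30% to 70%, and is zero at 50%. The size in this trial depends on surveillance rates and a risk mix that the documents do not give. The chart-review inconsistency is a separate and smaller matter affecting the same endpoint. Both concern secondary results; the primary knowledge analysis is untouched.

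**What to change.** 1. In 12.4.2, prespecify an exploratory secondary analysis of utilization by disease-risk group: a logistic mixed model of active surveillance versus surgery/radiation, with each aid, risk group, the aid-by-risk interactions and the random site intercept. Report estimates within risk group, and show the three treatment categories descriptively within each group.
2. Define a risk grouping that classifies every eligible man from Gleason score, stage and PSA. The descriptions in 1.1 do not: organ-confined Gleason 8-10, and T3 with Gleason 6 or 7, fall in no group.
3. State that precision is limited with 172 men in about 20 sites, and that the analysis is exploratory, as 12.4.2 already does for race/ethnicity.
4. Reconcile the section 5.0 footnote with 8.3.2 and 12.4.1 so that utilization data cover the whole period from the consultation to 12 months.

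The cost is some analysis-plan text, an agreed risk definition and one calendar footnote. Eligibility already requires the three risk variables, so no new patient assessment is needed, though the team should confirm that the values are held in the trial database. Estimates within risk group will be less precise than the overall comparison.

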12.5 Monitoring

12.5.1 Adverse Event Stopping Rules

This is a behavioral intervention, questionnaire-based outcome study (i.e., this is not a therapeutic study) and as such, no adverse event stopping rule will be developed (see Section 9.0).

12.5.2 Accrual Monitoring Stopping Rule

There is no formal plan to monitor for slow accrual. Meetings to assess recruitment will be conducted monthly. Regulatory DSMB reports will allow decisions to be made regarding stopping.

12.5.3 Other Monitoring

Conference calls (or webinars, if visual media is shared) will be arranged and conducted on an as-needed basis. These meetings will be led by the study chair, and will include the study statistician, protocol coordinator, institutional study coordinators and site investigators or their designees to monitor accrual, completeness of data collection, and safety.

12.6 Reporting

This study will be monitored by the Alliance Data and Safety Monitoring Board (DSMB), an NCI-approved functioning body. Reports containing efficacy, adverse event, and administrative information will be provided to the DSMB every 6 months as per NCI guidelines. Reports from these meetings will be made available to the study chair, statistician, and participating institutions.

Results Reporting on ClinicalTrials.gov: At study activation, this study will have been registered within the “ClinicalTrials.gov” website. The Primary and Secondary Endpoints along with other required information for this study will be reported on ClinicalTrials.gov.

12.7 Inclusion of Women and Minorities

Because prostate cancer occurs primarily in men above the age of 50, recruitment of participants for this study will focus upon men aged 50 years and older. Since women and children are not subject to prostate cancer, they will be excluded from this study.

Racial Categories	DOMESTIC PLANNED ENROLLMENT REPORT				
	Ethnic Categories				Total
	Not Hispanic or Latino		Hispanic or Latino		
	Female	Male	Female	Male	
American Indian/Alaska Native	0	43	0	0	43
Asian	0	5	0	0	5
Native Hawaiian or Other Pacific Islander	0	2	0	0	2
Black or African American	0	38	0	5	43
White	0	38	0	37	75
More Than One Race	0	3	0	1	4
Total	0	129	0	43	172

13.0 GENERAL REGULATORY CONSIDERATIONS AND CREDENTIALING

13.1 Limited Access requirements

Institutions that are interested in participating in this study must first contact the Study Chair, [name] to review study requirements and procedures and to identify who will be responsible for the study at the institution.

Criteria for participation will be based on the following:

- Site must provide consultation to newly diagnosed prostate cancer patients
- Site must have providers willing to use a decision aid in patient consults
- Site must be able to recruit 8-10 patients over 2 years
- 2-3 of those recruited each year need to self-identify as being from one of two groups: American Indian or Alaska Native (i.e. can be “more than one race” with one of those races being American Indian/Alaska Native) OR African American
- Sites that see a lot of Hispanic/Latino patients are encouraged to participate, however the trial materials and outcome measures require English speaking capacity or assistance by an appropriate translator.

14.0**REFERENCES**

APPENDIX I BASELINE QUESTIONNAIRE BOOKLET

Prostate Cancer Treatment Questionnaire

Please check the TRUE or FALSE box for each statement based on your knowledge of prostate cancer treatments. If you are not completely sure, mark 'Unsure'.

	True	False	Unsure
1. Most prostate cancer spreads quickly to other parts of the body	 1	 2	 3
2. Other illnesses can make treating prostate cancer more difficult	 1	 2	 3
3. Some treatments are better than others at stopping prostate cancer	 1	 2	 3
4. Radiation therapy from a machine for prostate cancer requires weeks of daily treatments	 1	 2	 3
5. Radiation seed therapy for prostate cancer requires weeks of daily treatments	 1	 2	 3
6. Radiation for prostate cancer can cause rectal pain	 1	 2	 3
7. Surgery for prostate cancer can cause urine leakage	 1	 2	 3
8. For most men, radiation therapy for prostate cancer has no effect on urinary control	 1	 2	 3
9. Both surgery and radiation can decrease sexual function	 1	 2	 3
10. Low-risk prostate cancer can be safely monitored	 1	 2	 3
11. After prostate cancer surgery, a man will go home with a catheter	 1	 2	 3
12. Hot flashes is a side-effect of hormone treatment	 1	 2	 3

Investigator developed.

Decisional Conflict Scale*My difficulty in making this choice***A. Which treatment option do you prefer? Please check one.**

- Surgery
- Radiation (includes Brachytherapy, IMRT, proton beam)
- Active Surveillance (also called watchful waiting)
- Unsure

B. Considering the option you preferred, please answer the following questions:

	Yes	Unsure	No
1. Do you know which options are available to you?			
2. Do you know the benefits of each option?			
3. Do you know the risks and side effects of each option?			
4. Are you clear about which benefits matter most to you?			
5. Are you clear about which risks and side effects matter most to you?			
6. Do you have enough support from others to make a choice?			
7. Are you choosing without pressure from others?			
8. Do you have enough advice to make a choice?			
9. Are you clear about the best choice for you?			
10. Do you feel sure about what to choose?			

Decisional Conflict Scale © AM O'Connor, 1993, revised 2005

APPENDIX II FOLLOW-UP (12-MONTH) QUESTIONNAIRE BOOKLET

Expanded Prostate Cancer Index Composite—Short Form (EPIC-26)

This questionnaire is designed to measure Quality of Life issues in patients with Prostate cancer. To help us get the most accurate measurement, it is important that you answer all questions honestly and completely.

1. Over the **past 4 weeks**, how often have you leaked urine?

- More than once a day
- About once a day
- More than once a week
- About once a week
- Rarely or never

2. Which of the following best describes your urinary control **during the last 4 weeks**?

- No urinary control whatsoever
- Frequent dribbling
- Occasional dribbling
- Total control

3. How many pads or adult diapers per day did you usually use to control leakage **during the last 4 weeks**?

- None
- 1 pad per day
- 2 pads per day
- 3 or more pads per day

4. How big a problem, if any, has each of the following been for you **during the last 4 weeks?**

	No Problem	Very Small Problem	Small Problem	Moderate Problem	Big Problem
a. Dripping or leaking urine					
b. Pain or burning on urination					
c. Bleeding with urination					
d. Weak urine stream or incomplete emptying					
e. Need to urinate frequently during the day					

5. Overall, how big a problem has your urinary function been for you **during the last 4 weeks?**

- No problem
- Very small problem
- Small problem
- Moderate problem
- Big problem

6. How big a problem, if any, has each of the following been for you?	No Problem	Very Small Problem	Small Problem	Moderate Problem	Big Problem
					
a. Urgency to have a bowel movement					
b. Increased frequency of bowel movements					
c. Losing control of your stools					
d. Bloody stools					
e. Abdominal/ Pelvic/ Rectal pain					

7. Overall, how big a problem have your bowel habits been for you **during the last 4 weeks?**

- No problem
- Very small problem
- Small problem
- Moderate problem
- Big problem

8. How would you rate each of the following during the last 4 weeks?	Very poor to none	Poor	Fair	Good	Very Good
					
a. Your ability to have an erection?					
b. Your ability to reach orgasm (climax)?					

9. How would you describe the usual **QUALITY** of your erections **during the last 4 weeks?**

- None at all
- Not firm enough for any sexual activity
- Firm enough for masturbation and foreplay only
- Firm enough for intercourse

10. How would you describe the **FREQUENCY** of your erections **during the last 4 weeks?**

- I NEVER had an erection when I wanted one
- I had an erection LESS THAN HALF the time I wanted one
- I had an erection ABOUT HALF the time I wanted one
- I had an erection MORE THAN HALF the time I wanted one
- I had an erection WHENEVER I wanted one

11. Overall, how would you rate your ability to function sexually **during the last 4 weeks?**

- Very poor
- Poor
- Fair
- Good
- Very good

12. Overall, how big a problem has your sexual function or lack of sexual function been for you **during the last 4 weeks?**

- No problem
- Very small problem
- Small problem
- Moderate problem
- Big problem

13. How big a problem **during the last 4 weeks**, if any, has each of the following been for you?

	No Problem	Very Small Problem	Small Problem	Moderate Problem	Big Problem
--	------------	--------------------	---------------	------------------	-------------

- a. Hot flashes

				
--------------------------	--------------------------	--------------------------	--------------------------	--------------------------
- b. Breast tenderness / enlargement

				
--------------------------	--------------------------	--------------------------	--------------------------	--------------------------
- c. Feeling depressed

				
--------------------------	--------------------------	--------------------------	--------------------------	--------------------------
- d. Lack of energy

				
--------------------------	--------------------------	--------------------------	--------------------------	--------------------------
- e. Change in body weight

				
--------------------------	--------------------------	--------------------------	--------------------------	--------------------------

Decisional Regret Scale

Please think about the decision you made about how to treat your prostate cancer after talking to your doctor. Please show how you feel about these statements by circling a number from 1 (strongly agree) to 5 (strongly disagree).

	Strongly Agree	Agree	Neither Agree nor Disagree	Disagree	Strongly Disagree
1. It was the right decision	1	2	3	4	5
2. I regret the choice that was made	1	2	3	4	5
3. I would go for the same choice if I had to do it over again	1	2	3	4	5
4. The choice did me a lot of harm	1	2	3	4	5
5. The decision was a wise one	1	2	3	4	5

Decision Regret Scale © AM O'Connor, 1996 University of Ottawa
